2.5.3 Handling of missing values/censoring/discontinuations

Patients who discontinued prematurely for any reason will be considered non-responders from the time they discontinued. Patients who do not have the required data to compute ACR20 response (i.e., tender and swollen joint counts and at least three of the five ACR components) at baseline and at the specific time point will be classified as non-responders.

In an additional analysis, missing data for ACR20 response variable will be handled by multiple imputation. Multiple imputation is a simulation-based approach where missing values are replaced by multiple Bayesian draws from the conditional distribution of missing data given the observed data and explanatory variables, creating multiple completed data sets. These completed data sets can then be analyzed using standard methods. Within this analysis, the ACR components will be imputed and response variables will be derived based on the imputed scores. In the multiple imputation analysis, the response status will be imputed based on the individual treatment arm information.

2.5.4 Supportive analyses

The primary efficacy variable will also be analyzed at each time point till Week 16 for the Full Analysis Set using the Cochran-Mantel-Haenszel (CMH) test to compare secukinumab 300 mg against placebo, adjusting for methotrexate usage at baseline (yes, no) (Stokes, Davis, and Koch, 2012).

If the treatment comparison p-value is < 0.05 and the proportion of patients who are ACR20 responders is higher in a secukinumab treatment group compared to the placebo treatment group, statistical significance in favor of that dose of secukinumab is shown. Two 95% confidence intervals for the difference between each dose of secukinumab versus placebo in the proportion of patients who are ACR20 responders will be calculated using the normal approximation to the binomial distribution.

2.6 Analysis of the key secondary objective

There is no key secondary objective.

2.7 Analysis of secondary efficacy objective(s)

Refer to Table1.2-1 of Section 1 for the list of secondary objectives.

2.7.1 Secondary endpoints

All the secondary efficacy evaluation will be performed on FAS.

The secondary efficacy variables are the following:

- 1. Dactylitis (yes, no)
- 2. Enthesitis (yes, no)
- 3. ACR50 response (yes, no)

- 4. ACR70 response (yes, no)
- 5. Minimal Disease Activity (yes, no)
- 6. PASI75 response (yes, no)
- 7. PASI90 response (yes, no)
- 8. PASI100 response (yes, no)
- 9. Change from baseline in DAS28-CRP
- 10. Change from baseline in PASDAS
- 11. Change from baseline in SF12
- 12. Change from baseline in HAQ-DI

2.7.2 Statistical hypothesis, model, and method of analysis

Dactylitis and enthesitis

Analyses of dactylitis and enthesitis will be performed at each time point up to Week 16. The data for the subgroup of patients who have dactylitis at baseline (similarly for enthesitis) will be used and the data will be analyzed using a logistic regression model with treatment (3 treatment groups), methotrexate usage at baseline (yes, no), and body weight as explanatory variables. The odds ratios for each dose of secukinumab versus placebo, 95% confidence interval for the odds ratios, and p-values based on the fitted model will be reported.

Number and percentages of patients with presence of enthesitis will be reported for each treatment group and by visit in entire treatment period up to Week 52. Similar summary will be provided for patients with presence of enthesitis using non-responder imputation.

The above analyses will be done on Dactylitis Subset,

ACR20, ACR50, and ACR70 responses

ACR20, ACR50, ACR70 responses at each time point up to Week 16, and in subsets of patients with active PsA and number of tender and swollen joints < 10 and ≥ 10 at baseline will be analyzed using a logistic regression model with treatment (3 treatment groups), methotrexate usage at baseline (yes, no), and body weight as explanatory variables. The odds ratios for each dose of secukinumab versus placebo, 95% confidence intervals for the odds ratios, and p-values based on the fitted model will be reported.

Additionally, ACR50 and ACR70 responses will be analyzed as analogous to primary efficacy variable at each time point up to Week 16.

Number and percentages of ACR50 and ACR70 responders will be reported for each treatment group, concomitant methotrexate usage at baseline and by visit in entire treatment period up to Week 52. Similar summary will be provided for ACR50 and ACR70 using non-responder imputation.

Number and percentages of ACR50 and ACR70 responders in subsets of patients with active PsA and number of tender and swollen joints < 10 and \geq 10 at baseline will be reported for each treatment group and by visit in entire treatment period up to Week 52. Similar summary will be provided for ACR50 and ACR70 using non-responder imputation.

Minimal Disease Activity

Minimal Disease Activity response at each time point up to Week 16 will be analyzed using a logistic regression model with treatment (3 treatment groups), methotrexate usage at baseline (yes, no), and body weight as explanatory variables. The odds ratios for each dose of secukinumab versus placebo, 95% confidence intervals for the odds ratios, and p-values based on the fitted model will be reported.

Number and percentages of Minimal Disease Activity response will be reported for each treatment group and by visit in entire treatment period up to Week 52. Similar summary will be provided for Minimal Disease Activity response using non-responder imputation method.

Very Low Disease Activity

Very Low Disease Activity (yes, no) is achived when 7 out of the following 7 criteria are met: ≤ 1 tender joint, ≤ 1 swollen joint, PASI ≤ 1 or IGA mod 2011 ≤ 1 , patient assessment of pain (0-100 Visual Analog Scale (VAS)) ≤ 15 , patient global assessment of disease (VAS) ≤ 20 , HAQ-DI ≤ 0.5 , tender entheseal points ≤ 1 .

Very Low Disease Activity response at each time point up to Week 16 will be analyzed using a logistic regression model with treatment (3 treatment groups), methotrexate usage at baseline (yes, no), and body weight as explanatory variables. The odds ratios for each dose of secukinumab versus placebo, 95% confidence intervals for the odds ratios, and p-values based on the fitted model will be reported.

Number and percentages of Very Low Disease Activity response will be reported for each treatment group and by visit in entire treatment period up to Week 52 for the observed data. Similar summary will be provided for Very Low Disease Activity response using non-responder imputation method.

PASI75, PASI90, PASI100 responses

Response to PASI75, PASI90, PASI100 at each time point up to Week 16 will be analyzed using a logistic regression model with treatment (3 treatment groups), methotrexate usage at baseline (yes, no), and body weight as explanatory variables. The odds ratios for each dose of secukinumab versus placebo, 95% confidence intervals for the odds ratios, and p-values based on the fitted model will be reported.

Novartis	For business use only	Page 28
SAP		Secukinumab/AIN457FUS01

The above analyses will be done on Psoriasis Subset.

Number and percentages of PASI75, PASI90, and PASI100 responders will be reported for each treatment group and by visit in entire treatment period up to Week 52. Similar summary will be provided for PASI75, PASI90, and PASI100 responders using non-responder imputation method.

DAS28-CRP

The change from baseline in DAS28-CRP at each time point up to Week 16 will be analyzed by an analysis of covariance (ANCOVA) model with treatment (3 treatment groups), baseline, methotrexate usage at baseline (yes, no), and body weight as explanatory variables. The least squares means (LS Means) of the three treatment groups, least squares mean differences between each dose of secukinumab and placebo, 95% confidence intervals for the difference between each dose of secukinumab and placebo, and p-values based on the fitted linear model will be reported.

Summary statistics for observed DAS28-CRP score and change from baseline in score will be reported for each treatment group and by visit in entire treatment period up to Week 52.

PASDAS

The change from baseline in PASDAS at each time point up to Week 16 will be analyzed by an analysis of covariance (ANCOVA) model with treatment (3 treatment groups), baseline, methotrexate usage at baseline (yes, no), and body weight as explanatory variables. The least squares means (LS Means) of the three treatment groups, least squares mean differences between each dose of secukinumab and placebo, 95% confidence intervals for the difference between each dose of secukinumab and placebo, and p-values based on the fitted linear model will be reported.

Summary statistics for observed PASDAS score and change from baseline in score will be reported for each treatment group and by visit in entire treatment period up to Week 52.

SF12

Refer to Section 2.11.

HAQ-DI

Refer to Section 2.11.

Summary statistics will include relative and absolute frequencies for the binary variable (ACR20, ACR50, ACR70, dactylitis, enthesitis, Minimal Disease Activity, Very Low Disease Activity, PASI75, PASI90, PASI100) and the number of patients (N), mean, standard deviation,

median, 25th and 75th percentiles, interquartile range, minimum, and maximum for the continuous variables (DAS28-CRP, PASDAS, etc.,) for each treatment group and by visit. Graphical representation will also be performed if required.

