6.4.11 Dactylitis Assessments

[REDACTED]

[REDACTED]

Presence of dactylitis

If dactylitis is present with any finger or toe, the subject is counted as a subject with dactylitis.

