6.4.12 Enthesitis Assessments

Presence of enthesitis:

If enthesitis is present with any of the 18 sites below, the subject is counted as a subject with enthesitis.

- Medial epicondyle humerus (left/right (L/R))
- Lateral epicondyle humerus (L/R)
- Supraspinatus insertion into greater tuberosity of humerus (L/R)
- Greater trochanter (L/R)
- Medial condyle femur (L/R)
- Quadriceps insertion into superior border of patella (L/R)
- Patellar ligament insertion into inferior pole of patella or tibial tubercle (L/R)
- Achilles tendon insertion into calcaneum (L/R)
- Plantar fascia insertion into calcaneum (L/R)

[REDACTED]

[REDACTED]

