9.7 Sample size calculation

The sample size was calculated based on the primary efficacy variable (i.e., ACR20 response) for the primary comparison (i.e., secukinumab 300 mg versus placebo). ACR20 response rates of 50% for secukinumab 300 mg and 20% for placebo (corresponding to an odds ratio of 4) at Week 16 were assumed, based on results from AIN457F2312 (FUTURE 2) study. Using a continuity-corrected chi-squared test, an allocation ratio of 2:1, a two-sided significance level of 0.05, and a power of 0.90, approximately 88 patients in secukinumab 300 mg group and 44 patients in placebo group will be needed (nQuery Advisor 7.0). Assuming a loss to follow-up rate of 10% and a 2:2:1 allocation ratio (secukinumab 300 mg: secukinumab 150 mg: placebo), the total number of randomized patients will be approximately 250 (100 on secukinumab 300 mg, 100 on secukinumab 150 mg, and 50 on placebo)

10 Ethical considerations

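### The dactylitis and enthesitis models leave out the baseline number of affected digits or sites; the planned test is valid, but adjusting for the count would add an estimated 1 to 8 points of power for 300 mg versus placebo, under assumptions.

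*SAP*

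**What the plan says.** Protocol 2.2 lists dactylitis and enthesitis at Week 16 as secondary objectives. Each dose is compared with placebo among patients who had the finding at baseline.

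The endpoints are defined by presence anywhere:
- Protocol 6.4.11: "If dactylitis is present with any finger or toe, the subject is counted as a subject with dactylitis".
- Protocol 6.4.12: "If enthesitis is present with any of the 18 sites below, the subject is counted as a subject with enthesitis".

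SAP 2.7.2 restricts to the baseline-positive subset ("The data for the subgroup of patients who have dactylitis at baseline (similarly for enthesitis) will be used and the data will be analyzed") and fits the data "using a logistic regression model with treatment (3 treatment groups), methotrexate usage at baseline (yes, no), and body weight as explanatory variables". Protocol 9.5.1 has the same covariates, and the logistic code in SAP 5.4.1, which SAP 5.4.3 applies to categorical secondary endpoints, has no baseline term.

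Four other provisions bear on the point:
- SAP 2.5.2 justifies methotrexate and weight as covariates by their possible influence on the outcome, although neither is a stratification factor.
- SAP 1.1 says that randomization is not stratified.
- SAP 2.7.3 applies non-responder imputation to these binary endpoints.
- The SAP revision history contains entries dated after the Week 16 database lock.

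**The concern.** Success here means zero affected digits or sites at Week 16. If each affected site cleared independently with probability p, a patient with one site would succeed with probability p and a patient with ten sites with probability p to the tenth power. Correlation between sites within a patient weakens this gradient but does not remove it. The baseline count therefore meets the SAP's own test for including a covariate at least as well as methotrexate or weight does.

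Two things are at stake. The first is power: the subsets are only part of a trial sized for ACR20 in all patients, and placebo is one fifth of each subset. The second is robustness: with few placebo patients and no stratification, baseline burden can differ between arms by chance, and the planned odds ratio does not correct for it.

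**Working it through.** **The plan's own sizing.** Protocol 9.7 assumes "ACR20 response rates of 50% for secukinumab 300 mg and 20% for placebo", "Using a continuity-corrected chi-squared test, an allocation ratio of 2:1, a two-sided significance level of 0.05, and a power of 0.90". With placebo rate 0.20, active rate 0.50, r = 2 and pooled rate (0.20 + 2 × 0.50)/3 = 0.40:

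- Uncorrected placebo n = [1.960·√(3 × 0.24) + 1.282·√(2 × 0.16 + 0.25)]² / (2 × 0.30²) = 2.631²/0.18 = 38.4, so 39 and 78.
- Continuity-corrected n = (38.4/4)·[1 + √(1 + 6/(38.4 × 2 × 0.30))]² = 43.3, so 44 and 88.

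This reproduces "approximately 88 patients in secukinumab 300 mg group and 44 patients in placebo group will be needed". Dividing by 0.9 for 10% loss gives 49 and 98, in line with the planned 50 and 100. No comparable calculation exists for dactylitis or enthesitis.

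**Inputs that the documents do not give (all assumed).** These are subset sizes, resolution rates, count distributions and the strength of the count as a predictor. Two simulations with different structures were used.

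**Simulation A: count effect imposed directly.** Subsets were 30–50% (dactylitis) and 50–70% (enthesitis) of 100/100/50. Resolution was 20–35% on placebo and 40–65% on 300 mg, with 150 mg midway. Counts were truncated geometric, with mean 4 of 20 digits and 4.5 of 18 sites. Each scenario had 3000 trials and a two-sided 0.05 Wald test. The SAP model was fitted with and without standardized log count, holding marginal rates fixed. Power under the SAP model was about 31–84% for 300 mg. Power gain in percentage points:

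| Odds ratio of non-resolution per SD of log count | 300 mg v placebo | 150 mg v placebo |
|---|---|---|
| 1.0 | −0.5 to +0.7 | about 0 |
| 1.5 | +0.8 to +3.0 | about 0 to +1 |
| 2.0 | +2.9 to +5.1 | +0.8 to +3.4 |
| 2.5 | +4.8 to +8.1 | +1.6 to +4.3 |
| 3.0 | +6.3 to +10.3 | +2.5 to +6.3 |

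**Which odds ratio is plausible?** A site-level model, in which every affected site must clear and sites share a normal patient effect, gives these odds ratios per SD of log count:
- independent sites: 4.0–4.5
- patient-effect SD 1: 2.9–3.0
- SD 2: 2.0–2.1
- SD 4: about 1.5

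**Simulation B: site-level design, 300 mg v placebo.** Enthesitis used 70/70/35 patients, mean count 4–5 and clearance about 60% v 36%. Dactylitis used 45/45/22 patients, mean count 3 and clearance 64% v 34%. Power without the count was about 0.64 for each. Gain in points, with marginal rates held fixed:

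| Patient-effect SD and failure sources | Enthesitis | Dactylitis |
|---|---|---|
| SD 1, no dropout, no new sites | +7.2 to +7.6 | +5.4 to +5.6 |
| SD 1, 10% dropout counted as failure | +5.9 | +4.6 |
| SD 1, 10% dropout and 10% new-site failure | +4.0 | +2.8 |
| SD 2, both | +2.1 | +0.9 |
| SD 3, both | about +1 | about +1 |

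The 10% dropout figure is the plan's ("Assuming a loss to follow-up rate of 10% and a 2:2:1 allocation ratio"); the 10% new-site failure is assumed. Repeat runs move individual entries by around a point. One-sided type I error was 0.025 without the count and 0.027 with it.

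**Chance imbalance.** A difference between 300 mg and placebo in mean standardized log count at the 95% limit is 1.96·√(1/n₁ + 1/n₂). If the odds ratio is 2 per SD (assumed), the planned odds ratio shifts by about 2 raised to that difference:
- Dactylitis: 1.96·√(1/22 + 1/45) = 0.51 SD, a factor of about 1.4.
- Enthesitis: 1.96·√(1/35 + 1/70) = 0.41 SD, a factor of about 1.3.

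**The case against.** **This is not an error.** One common model was prespecified for the binary endpoints, and the PASI and Minimal Disease Activity models carry no baseline term either. SAP 2.6 names no key secondary objective, and only ACR20 was powered. All of this stands. A reader might infer that the planned test is invalid or biased. It is not: randomization protects type I error, and the simulation showed no material difference.

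**The contrast with ANCOVA is weak.** The continuous endpoints are adjusted for their own baseline, so a reader might see an inconsistency. In these subsets, however, the binary baseline value is already fixed at yes. The case for the count comes from the any-site definition, not from symmetry with ANCOVA.

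**The size is not a property of the plan.** A reader might infer that the count is the main predictor, or that a fixed number of points is lost. The documents neither rank predictors nor give the inputs. Dropouts count as failures whatever their baseline count. Newly affected sites also count as failures, and Protocol 9.5.1 has an ordinal category that includes new onset. Both dilute the gain, as the second table shows.

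**Availability is partly inference.** The visible text of Protocol 6.4.12 defines presence only, and what follows the list is redacted. Still, an 18-site rule cannot be applied without examining the sites, and PASDAS in Protocol 6.4.9 needs a dactylitis count. Its enthesitis term is a Leeds count, which the documents do not equate with the 18-site count. SAP 2.13 is cited in the revision history but is not in the public text, so count-based analyses there cannot be excluded.

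**Timing.** SAP 2.1 has the analysts unblinded at the Week 16 lock. Replacing the planned Week 16 model after that would be a post-unblinding change. This stands and limits the fix.

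**Conclusion.** The omission is real in both documents and concerns two named secondary objectives. It is a missed improvement in efficiency and robustness, not a flaw in validity.

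For 300 mg versus placebo, roughly 1 to 8 points of power is a fair summary: about 4 to 8 with modest within-patient correlation, and about 1 to 4 with strong correlation, dropout or new-site failures. In Simulation A, gains above about 8 points needed an odds ratio near 3 per SD, with no separate dropout or new-site failures. If the count had no prognostic value, the gain would be nil and the loss negligible (−0.5 to +0.7 points). For 150 mg, at half the assumed effect, the gain is about 0 to 6 points across odds ratios of 1.5 to 3.

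All these figures rest on assumed subset sizes, clearance rates, count distributions and predictor strength.

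**What to change.** In SAP 2.7.2 add one covariate to each model, beside treatment, methotrexate use and body weight:

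- Enthesitis: log of the baseline number of affected sites among the 18 in Protocol 6.4.12, not the Leeds count used in PASDAS.
- Dactylitis: log of the baseline number of dactylitic digits. SAP 2.2 defines the Dactylitis Subset by an LDI threshold, so confirm that every member has a count of at least one.

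If this is specified before Week 16 unblinding, make it the main model for these two endpoints and align Protocol 9.5.1. If the Week 16 data are already unblinded, keep the planned model and report the adjusted one beside it, labelled supplementary, with its date and reason. In either case state that the adjusted odds ratio is conditional on count and is not numerically interchangeable with the planned one. SAP section 4, which now lists no changes to the protocol-specified analyses, should record the addition.

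The cost is one term in each of two models, plus confirmation that site and digit counts are in the database. No new assessment should be needed.

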2.2 Secondary objectives

To evaluate:

- The efficacy of secukinumab 150 mg compared to placebo at Week 16 in patients with active PsA based on the proportion of patients achieving an American College of Rheumatology 20 (ACR20) response.
- The efficacy of secukinumab 300 mg and 150 mg compared to placebo at Week 16 based on the proportion of patients with dactylitis in the subset of patients who have dactylitis at baseline.
- The efficacy of secukinumab 300 mg and 150 mg compared to placebo at Week 16 based on the proportion of patients with enthesitis in the subset of patients who have enthesitis at baseline.
- The efficacy of secukinumab 300 mg and 150 mg compared to placebo at Week 16 in subset of patients with active PsA and number of tender and swollen joints less than 10 at baseline based on the proportion of patients achieving ACR20, ACR50, and ACR70 responses
- The efficacy of secukinumab 300 mg and 150 mg compared to placebo at Week 16 based on the proportion of patients achieving ACR50 and ACR70 responses.
- The efficacy of secukinumab 300 mg and 150 mg compared to placebo at Week 16 based on the proportion of patients achieving Minimal Disease Activity (5 of the following 7 criteria: ≤ 1 tender joint, ≤ 1 swollen joint, PASI ≤ 1 or IGA mod 2011 ≤ 1 , patient assessment of pain (0-100 Visual Analog Scale (VAS)) ≤ 15 , patient global assessment of disease (VAS) ≤ 20 , HAQ-DI ≤ 0.5 , tender enthesal points ≤ 1).
- The efficacy of secukinumab 300 mg and 150 mg compared to placebo at Week 16 based on the proportion of patients achieving a PASI75, PASI90, and PASI100 responses
- The efficacy of secukinumab 300 mg and 150 mg compared to placebo at Week 16 based on the change from baseline in DAS28-CRP.
- The efficacy of secukinumab 300 mg and 150 mg compared to placebo at Week 16 based on the change from baseline in Psoriatic Arthritis Disease Activity Score (PASDAS).
- The efficacy of secukinumab 300 mg and 150 mg compared to placebo at Week 16 based on the change from baseline in SF12.
- The efficacy of secukinumab 300 mg and 150 mg compared to placebo at Week 16 based on the change from baseline in HAQ-DI.

- The overall safety and tolerability of secukinumab 300 mg and 150 mg compared with placebo as assessed by vital signs, clinical laboratory values, and adverse events (AE) monitoring.

3 Investigational plan

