2.2 Analysis sets

The following analysis sets will be used for the statistical reporting and analyses:

Randomized Set: The Randomized Set includes all randomized patients.

Safety Set: The Safety Set includes all patients who received at least one dose of study medication. Patients will be included in the analysis according to treatment received.

Full Analysis Set (FAS): The Full Analysis Set comprises all patients to whom study medication has been assigned. Patients inappropriately randomized (e.g., IRT was called in error for randomization of a screen failed patient) will be excluded from this analysis set.

Psoriasis Subset: The Psoriasis Subset comprises patients in whom at least 3% of body surface area was affected by psoriatic skin involvement at baseline.

Dactylitis Subset: The Dactylitis Subset comprises patients who have LDI >= 1 at baseline.

Up-titrated Subset: Up-titration Subset includes all completed patients who were up-titrated from 150 mg to 300 mg in Treatment Period 2, based on the response.

For efficacy analyses, following the intent-to-treat principle, patients will be analyzed according to the treatment they were assigned to at randomization.

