2.2.1 Subgroup of interest

Planned subgroups of interest are the subsets defined in Section 2.2.

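### SAP 2.7.2 gives contradictory populations for the enthesitis analyses, and no Enthesitis Subset is defined to settle which applies

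*SAP*

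**What the plan says.** **Protocol.** Section 2.2 sets the enthesitis objective on the "proportion of patients with enthesitis in the subset of patients who have enthesitis at baseline". Section 6.4.12 defines presence: "If enthesitis is present with any of the 18 sites below, the subject is counted as a subject with enthesitis". Section 9.5.1 repeats the principle that each sign is analysed in the patients who have that sign at baseline.

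**SAP.** Section 2.7.2 treats both signs under one joint heading. For the logistic model up to Week 16 it says: "The data for the subgroup of patients who have dactylitis at baseline (similarly for enthesitis) will be used". The next paragraph turns to enthesitis alone, with summaries that run to Week 52: "Number and percentages of patients with presence of enthesitis will be reported for each treatment group and by visit in entire treatment period up to" (quoted in part). A second version uses non-responder imputation. The joint text then closes with "The above analyses will be done on Dactylitis Subset", followed by a comma and nothing further.

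SAP 2.2 lists a Psoriasis Subset, a Dactylitis Subset and an Up-titrated Subset. The second is defined so: "The Dactylitis Subset comprises patients who have LDI >= 1 at baseline". No Enthesitis Subset appears in the visible text. Section 2.2.1 adds: "Planned subgroups of interest are the subsets defined in Section 2.2". Section 2.7.1 assigns all secondary efficacy evaluation to the Full Analysis Set (FAS).

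**The concern.** The closing sentence refers back to everything above it, and what stands immediately above it concerns enthesitis only. A programmer has reason to take it as an instruction, because the same construction, naming the Psoriasis Subset, is used for the PASI responses in the same section and is plainly meant there.

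The Week 16 enthesitis model would then be tied to the wrong sign, or to patients with both signs. The Week 52 summaries would be tabulated in patients chosen for dactylitis. Resolution of enthesitis is a stated secondary objective, and Protocol 1.2 names enthesitis in the purpose of the study. SAP section 4 declares no change from the protocol's analyses, so nothing indicates that a different population was intended.

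**Working it through.** **1. Plan's own figure.** None exists for this point. The only sizing, in Protocol 9.7, is for ACR20. It reproduces (44 placebo and 88 on 300 mg; 44/0.9 gives 49; 5 × 49 = 245, stated as about 250) and plays no part here.

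**2. Populations that the text supports for enthesitis**

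- A: patients with enthesitis at baseline (Protocol 2.2 and 9.5.1; opening of SAP 2.7.2).
- B: the Dactylitis Subset, whatever the enthesitis status (literal reading of the closing sentence, most natural for the Week 52 summaries, which name no other subgroup).
- C: patients with both signs (opening and closing sentences applied together to the Week 16 model).
- D: the FAS (SAP 2.7.1).

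A and D are compatible if A is read as FAS patients with enthesitis at baseline. B and C conflict with the objective.

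**3. Size of the difference.** Inputs from Protocol 9.7: N = 250, as 100/100/50. Assumed, because the documents give no prevalences: a share e = 40–80% has enthesitis at baseline, a share d = 20–50% has dactylitis, and the two are independent.

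| Quantity | Formula | Total | Placebo | Each active arm |
|---|---|---|---|---|
| Target set (A) | N·e | 100–200 | 20–40 | 40–80 |
| Dactylitis Subset (B) | N·d | 50–125 | 10–25 | 20–50 |
| Both signs (C) | N·e·d | 20–100 | 4–20 | 8–40 |

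- Target patients lost under B or C: 1 − (N·e·d)/(N·e) = 1 − d = 50–80%.
- Share of B without baseline enthesitis: 1 − e = 20–60%.
- Central case (e = 60%, d = 35%): 250 × 0.60 = 150 target patients; 250 × 0.35 = 87.5 in the Dactylitis Subset; 87.5 × 0.60 = 52.5 with both. Loss = 97.5/150 = 65%. Without enthesitis in B: 35/87.5 = 40%.

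**4. Sensitivity to independence.** With the greatest possible overlap, the share kept is min(e, d)/e. In the central case that is 0.35/0.60 = 58%, so 42% are lost. At e = 80%, d = 20% the loss is 75%. At e = 40%, d = 50% it is zero.

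**5. Effect on the contrast under B.** Let p be an arm's proportion with enthesitis at Week 16 among patients positive at baseline, and u the same among those negative at baseline. The arm's overall proportion is e·p + (1 − e)·u. If u is close to 0 in every arm, the difference from placebo is e times the difference among the baseline-positive, so 0.4 to 0.8 of it. The unadjusted odds ratio becomes (p1/p0)·(1 − e·p0)/(1 − e·p1), which moves towards the risk ratio p1/p0 and so towards 1. New onset, or missing values imputed as unfavourable, would make u larger than 0. Under C there is loss of patients but no such dilution.

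**The case against.** The strongest reply is that the SAP already states the right population. The opening of 2.7.2 gives it for the inferential analysis up to Week 16, the objectives table in SAP 1.2 agrees, and SAP 2.3 plans baseline tables for patients with enthesitis. The sentence relied on is visibly unfinished, and words naming an enthesitis set may have been lost. Section 2.2.1 is not exclusive in practice either, since the SAP also plans analyses by baseline joint count, a grouping absent from 2.2.

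Much of this stands. The defect is a contradiction, not a settled wrong population, and the missing end of the sentence is not itself an error. But the reply does not resolve the contradiction. The opening sentence covers the Week 16 model, while the Week 52 summaries have no sign-specific population except the one in the closing sentence. Even if lost words pointed to an enthesitis set, the visible list in 2.2 contains none.

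A reader might infer more than the documents support, in two ways.

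- **That dactylitis is also analysed in the wrong patients.** The subset uses LDI >= 1, while Protocol 6.4.11 says "If dactylitis is present with any finger or toe, the subject is counted as a subject with dactylitis". The wording differs, but the scoring of LDI is not visible. Protocol 6.4.9 labels the dactylitis component of PASDAS as LDI and then enters a dactylitis count in the formula. If LDI acts as a count, the two definitions select the same patients. A mismatch is therefore not shown.
- **That patients without baseline enthesitis cannot respond.** The variable is presence of enthesitis. A patient who never had it falls in the favourable category in every arm. The harm is dilution, not built-in failure.

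**Conclusion.** The point holds as an internal contradiction about the enthesitis population, together with a dactylitis definition that needs confirmation. Followed literally, the closing sentence would lose 50–80% of the enthesitis-positive patients. That range rests on an assumed dactylitis prevalence of 20–50% and on independence of the two signs. Positive association would shrink the loss, to nothing in one extreme of the ranges examined, so the figure shows scale and is not an estimate for this trial. If the Dactylitis Subset were used without also requiring enthesitis, patients free of it at baseline would pull the comparison with placebo towards no difference. The documents do not show which set was used. Only secondary results are affected; the ACR20 analysis is untouched.

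**What to change.** - **SAP 2.2:** add an Enthesitis Subset, defined as FAS patients with enthesitis at one or more of the protocol's 18 sites at baseline.
- **SAP 2.7.2:** replace the closing sentence with two assignments: dactylitis analyses on the Dactylitis Subset; enthesitis analyses, including the Week 52 summaries with and without imputation, on the Enthesitis Subset.
- **SAP 2.7.1:** state that analyses restricted to a subset use FAS patients within it.
- **Dactylitis:** confirm in one line that LDI >= 1 selects the same patients as presence in at least one digit, or define the subset by presence.

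The text change is a few lines and needs no new data. The SAP's change log dates its latest updates (November and December 2018) after the Week 16 database lock, when SAP 2.1 allows statisticians and programmers to be unblinded. The correction should therefore be a dated, reasoned SAP change, citing the protocol objective as the source of the population. If Week 16 enthesitis results were already produced on another set, they should be rerun and the difference reported.
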